9.3.4.3. Patient Treatment Adherence

The duration of patients on TDF treatment and the primary reason of discontinuation will be summarized using descriptive statistics as appropriate. The difference between CHB patients who continued TDF and those who discontinued will be explored in terms of socio-demographic and clinical characteristics (e.g. baseline HBV DNA level, HBeAg status, baseline alanine aminotransferase level, receipt or no-receipt of previous treatment with other NUCs, previous history of drug resistance, treatment-naïve or experienced, ADV or non-ADV, type of baseline co-morbidities).

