To investigate patient adherence to therapy	Duration of TDF therapy during the study period

Objectives	Research Questions
	Summary of reasons of treatment discontinuation
To summarize the spontaneous AEs/SAEs and pregnancy exposures occurred during the study period (with special interest in AEs/SAEs due to TDF)	Summary of the occurrence of spontaneous AEs/ SAEs and pregnancy cases by GSK products and categorization.
	Incidence of decompensated cirrhosis/liver disease and related complications, at weeks of 48, 98 and 144

Abbreviations:

AEs = Adverse events; CHB = Chronic hepatitis B; CVR = Complete virological response; DNA = Deoxyribonucleic acid; eGFR = estimated Glomerular filtration rate; HBV = Hepatitis B virus; HBeAg = Hepatitis B envelope antigen; HCC = Hepatocellular carcinoma; MDRD = Modification of Diet in Renal Disease; SAEs = Serious adverse events * Sub-group of interest may include important baseline socio-demographic, health behaviour, and clinical characteristics.

According the relevance and importance to the clinical practice and patient outcomes, sub-groups are defined by patients sociodemographic, health behaviour and clinical characteristics and on treatment factors, including age, gender, baseline HBV DNA level, HBeAg status, baseline alanine aminotransferase level in relation to the upper limit of the normal range, receipt or no-receipt of previous treatment with other NUCs, previous history of drug resistance, comorbidities (e.g. chronic kidney disease, hypertension, diabetes), baseline renal function, patient treatment adherence, etc.

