8.2. Withdrawal from the Study

A participant may withdraw from the study at any time at his/her own request, or may be withdrawn at any time at the discretion of the investigator for safety, behavioral, compliance or administrative reasons. If the participant withdraws consent for disclosure of future information, the sponsor may retain and continue to use any data collected before such a withdrawal of consent.

In this real-world study, participants will be considered withdrawal from the study if any of the following events occurs within the 3-year study period:

Discontinuation of TDF (Viread, Beixin or Naxinde) for at least 28 days

Participation in clinical trials for any new drugs not limited to CHB-related ones during the 3-year study period

Study closed/terminated

Withdrew consent

The overall duration of TDF treatment and the reason for discontinuation of TDF treatment will be collected and the patient's adherence will be evaluated by the investigator a designed questionnaire.

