9.2. Populations for Analyses

The main population for analyses will consist of all consented participants who have the requested baseline data and at least one post-baseline assessment data.

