9.3. Statistical Analyses

A detailed Reporting and Analysis Plan (RAP) outlining details of data analyses will be created and described below. Besides the 144-week analysis, key analyses may be conducted annually with the 48-week and 96-week cut-off data to look at short-term patient outcomes. No adjustment for multiplicity will be made for these analyses.

Continuous variables will be summarized for overall population and various subgroups using mean (standard deviation) and/or median (range), while categorical variables will be summarized in tables of frequencies and percentages. Comparative analyses will be performed across sub-groups using Student's t test or analyses of variance for quantitative variables, and Pearson's Chi-square test (Fisher exact test might be used when necessary) for qualitative variables. Nonparametric tests will be used when necessary.

In primary and secondary analyses, as this is a real-world study without mandatory scheduled visits, the assessments (e.g. lab test) may not be conducted exactly at 6-month intervals, but to keep the robustness of the estimation for effectiveness and renal function change, a time window that ± 28 days for week 48, 96 and 144 will be applied in each cut-off analyses. As the supportive analyses, the analyses with time windows that ± 3 months will be conducted. More details will be included in Reporting and Analyses Plan (RAP).

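### TDF duration and discontinuation are planned as plain descriptive summaries, with no place for patients lost while still on TDF and a default population that may drop some early stoppers

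*Protocol*

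**What the plan says.** The research question in Protocol Section 4 is "Duration of TDF therapy during the study period", together with the reasons for stopping. Section 9.3.4.3 gives the analysis: "The duration of patients on TDF treatment and the primary reason of discontinuation will be summarized using descriptive statistics as appropriate". It adds a comparison of baseline characteristics between patients who continued and patients who discontinued. It names no population and no rule for patients whose TDF status becomes unknown.

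For continuous variables in general, Section 9.3 sets the mean with standard deviation, the median with range, or both. Section 9.2 defines one population: "The main population for analyses will consist of all consented participants who have the requested baseline data and at least one post-baseline assessment data".

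Under Section 8.2, one event that counts as study withdrawal is "Discontinuation of TDF (Viread, Beixin or Naxinde) for at least 28 days". Entering another drug trial and withdrawing consent are others. The same section provides that "The overall duration of TDF treatment and the reason for discontinuation of TDF treatment will be collected". Section 7.3 collects follow-up data every 6 months. Section 9.1.2 assumes 35% for loss to follow-up and discontinuation combined and does not split the figure. Section 9.3.4.2 plans Kaplan-Meier, log-rank and Cox methods, but for time to CVR.

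**The concern.** Two features of the plan act on the same summary.

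**Incomplete durations.** For a patient last seen on TDF at month 14 and then lost, 14 months is a minimum. A plain mean or median treats it as the finished duration. In the two-group comparison that patient has neither been shown to continue nor been recorded as stopping. Counting such patients as continued dilutes the contrast, and leaving them out makes it conditional on being followed. Patients already on TDF at entry (Section 6.1 caps them below 10%) raise a related problem. Their follow-up is anchored to TDF initiation (Section 2, note 6), but they could enrol only because they were still on treatment, so their early time on TDF could not have contained a stop.

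**Population.** Stopping TDF for 28 days ends participation. A new initiator who stops early may leave with no post-baseline assessment on file and so fall outside the Section 9.2 population. That patient is an event for this objective, and neither the stop date nor the reason depends on a laboratory value.

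The objective asks how long patients stay on TDF and why they stop. At stake are the discontinuation rate, the mix of reasons and the characteristics associated with stopping.

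**Working it through.** **Inputs from the Protocol.** N = 2000; 35% combined loss and discontinuation over 3 years; CVR 80% (all Section 9.1.2); 36 months of follow-up (Section 7.3).

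**The plan's own figure.** Completers: 2000 × 0.65 = 1300. Half-width: 1.96 × √(0.8 × 0.2 / 1300) = 0.0217, which agrees with the stated 2.2%. The protocol gives no figure for duration or discontinuation, so the rest is illustration.

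**Assumptions.** Exits occur at a constant hazard. A share f of exits is true TDF discontinuation and the rest is loss while on TDF. The Protocol does not give f, so it is varied. To represent the post-baseline requirement, everyone leaving before month 3 (or month 6) is taken to have no assessment, and everyone else to have one.

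**Hazard.** H = −ln(0.65)/3 = 0.1436 per year. With f = 0.5 the discontinuation hazard is h = 0.0718 per year.

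**Proportion discontinued by 3 years, f = 0.5**
- Kaplan-Meier target: 1 − exp(−3 × 0.0718) = 19.4%.
- Crude proportion of all enrolled: 0.5 × 35% = 17.5%.
- Still followed at month 3: exp(−0.1436 × 0.25) = 0.9647. Proportion after exclusion: 0.5 × (0.9647 − 0.65)/0.9647 = 16.3%.
- Still followed at month 6: exp(−0.1436 × 0.5) = 0.9307. Proportion after exclusion: 0.5 × (0.9307 − 0.65)/0.9307 = 15.1%.

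**Mean time on TDF within 3 years, f = 0.5**
- Restricted mean: 0.1938/0.0718 = 2.70 years (32.4 months).
- Plain mean of recorded durations, all enrolled: 0.35/0.1436 = 2.44 years (29.3 months).
- Plain mean after exclusion at month 3 or month 6: 30.3 or 31.2 months.

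**Other splits** (plain mean of all enrolled is 29.3 months in every row)

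| f | Kaplan-Meier % | Crude %, all enrolled | Crude %, excluded at month 3 / 6 | Restricted mean, months | Plain mean, excluded at month 3 / 6 |
|---|---|---|---|---|---|
| 1 | 35.0 | 35.0 | 32.6 / 30.2 | 29.3 | 30.3 / 31.2 |
| 0.75 | 27.6 | 26.25 | 24.5 / 22.6 | 30.8 | 30.3 / 31.2 |
| 0.5 | 19.4 | 17.5 | 16.3 / 15.1 | 32.4 | 30.3 / 31.2 |
| 0.25 | 10.2 | 8.75 | 8.2 / 7.5 | 34.1 | 30.3 / 31.2 |

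**How many patients.** Exits before month 3: 2000 × (1 − 0.9647) ≈ 71. Exits before month 6: 2000 × (1 − 0.9307) ≈ 139, which is 20% of the 700 exits. At f = 0.5 about 69 of those 139 are discontinuations, or 3.5% of enrolled patients. If exits are front-loaded (Weibull shape 0.7 or 0.5, same 35% total), the month-6 count is 231 or 323. At f = 0.5, 350 patients are lost while on TDF and have no natural place in the two-group comparison.

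**Direction.** Exclusion lowers the simple proportion discontinued in every row, and ignoring censoring lowers it further whenever f is below 1. On mean duration the two effects oppose each other: exclusion raises it and ignoring censoring lowers it. The net sign depends on f.

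**The case against.** Much of this is protocol silence rather than a stated error. The wording in Section 9.3.4.3 leaves room for Kaplan-Meier, which is itself a descriptive summary, and Sections 9.3 and 9.3.5 leave detail to the RAP, which is not at hand. Section 9.3.4.3 does not invoke the Section 9.2 population, that population is called the main one rather than the only one, and the adverse-event summary in Section 9.3.4.4 uses another denominator. The objective is exploratory in a study without formal hypotheses. Kaplan-Meier also needs non-informative loss, which is doubtful when no visit is mandatory.

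Three stronger readings are tempting, and the document does not support them:
- *All of the earliest stoppers vanish.* The Schedule of Activities lists TDF treatment status among the regular assessments, so a recorded stop may itself qualify a patient. A routine test before the 6-month prompt would qualify as well. Only some early stoppers are at risk of exclusion.
- *Durations of 3-year completers are lower bounds.* The question in Section 4 is confined to the study period, so for completers the duration is complete.
- *Time on TDF is bound to be understated.* The table shows that the direction depends on the unknown split.

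What stands is that the written default is a mean or median with a two-way comparison, that patients lost on treatment fit neither, and that no set of all enrolled or treated patients is defined. The protocol names a time-to-event method for CVR and could do so here.

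**Conclusion.** The point holds as a worthwhile improvement to an exploratory analysis. Followed as written, the summary counts patients lost on TDF as having finished durations or leaves them unclassified, and it may omit some early stoppers. At a constant hazard with half of the 35% being discontinuation, reported 3-year discontinuation would be 17.5%, or 15.1% to 16.3% with early exits excluded, against 19.4%. The exclusion figures are the extreme case in which nobody leaving before the chosen month has an assessment. If recorded status updates count as assessments, the shortfall from exclusion shrinks towards nothing and only the censoring part remains. The split, the hazard shape and the exclusion month are assumptions; the Protocol supplies only the combined 35%. No direction can be claimed for mean duration. The primary effectiveness analyses do not depend on this point.

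**What to change.** In Section 9.3.4.3, and in the RAP:
- Use all enrolled TDF-treated patients for duration, discontinuation and reasons, and report how many have no post-baseline assessment.
- Estimate time from TDF start to discontinuation by Kaplan-Meier. Censor at loss to follow-up, consent withdrawal, entry into another trial or study end. Let patients already on TDF enter the risk set at study entry (delayed entry).
- Report cumulative incidence of discontinuation by main reason.
- Replace the continued-versus-discontinued comparison with log-rank or Cox comparisons of time to discontinuation by baseline characteristics, as Section 9.3.4.2 does for time to CVR.

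No new data are needed, since start dates, treatment duration and reasons for stopping are already collected (Sections 7.2, 7.3 and 8.2). The cost is a little more analysis work and an explicit assumption that loss to follow-up is non-informative.

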9.3.4.4. Spontaneous Adverse Events and Pregnancy Events

• Spontaneous AEs/SAEs will be summarized using descriptive statistics.

Adverse events will be assigned preferred terms and categorized into body systems according to the medical dictionary for regulatory activities (MedDRA) classification of the World Health Organisation terminology.

The proportion of subjects who experienced AEs will be calculated by dividing the number of subjects who experienced the AE during the treatment period by the number of subjects evaluable for safety analysis. Adverse events will be summarised by treatment group, and by body system and event within each body system. The following summaries of AEs will be provided:

All AEs.

All treatment related AEs.

All SAEs.

All treatment related SAEs.

All AEs leading to permanent discontinuation of study drug.

All AEs leading to permanent discontinuation from the study.

- Pregnancy events will be summarized using descriptive statistics. In addition, change from baseline of serum phosphate, serum creatinine, and creatinine clearance will also be summarized to evaluate the drug safety.
- The incidence of decompensated cirrhosis/liver disease and related complications, such as HCC, will be calculated for weeks of 48, 98 and 144, for the overall analysis population, and for certain sub-populations of interests, such as elderly and baseline Cirrhosis patients

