7.3. Follow Up Data Collection

Study participants will be followed up for 3 years or until they withdraw from the study. Follow-up information will be collected at 6-month intervals:

- Regular tests
 - o HBV serology
 - o HBV DNA
 - o Serum creatinine and eGFR [MDRD equation]
 - Serum phosphate
 - Alanine transaminase (ALT) and aspartate transaminase (AST)
- Other tests and procedures
 - o AFP
 - o Hepatic ultrasound
 - Genotype
 - o Bone mineral density

- Liver biopsy
- o Transient elastography (fibrotouch or fibroscan)
- Hepatic ultrasound /computed tomography (CT) /magnetic resonance imaging (MRI)
- Updated CHB treatment details, e.g. any change to regimen or dosage and reason for change
- Comorbidity and concomitant medication review
- Spontaneous AEs if available
- For treatment adherence, it will be evaluated by the treating physician according to the patients' care seeking care, e.g. whether take the medication as prescribed, have you ever discontinued your medications and for how long?
- For participants who discontinue TDF prematurely, duration of treatment and reasons for TDF discontinuation will be recorded, e.g. SAEs, non-SAEs, and insufficient effectiveness.

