9.1.2. Sample Size Assumptions

Sample sizes are estimated based on feasibility and precision level achieved as no formal hypothesis will be tested in this study.

The primary objective of this study is to assess the effectiveness of TDF, with one important indicator being the proportion of subjects who achieve the CVR (i.e. HBV-DNA undetectable) at weeks of 48, 96, and 144. To be able to assess the CVR achievement at week 144, a sample size of 2,000 patients will provide a precision of no more than 2.2%, assuming the percentage of patients achieving CVR is 80% and the rate of loss-to-follow-up and discontinuation is 35%. The precision is calculated by the following: precision = $Z_{(1\alpha/2)}$ *SQRT(p*(1-p)/N), where Z is the critical value of normal distribution corresponding to the probability of 1- α /2 (corresponding to (1- α)*100% confidence interval), and p is the percentage of patients achieving CVR. It is half of the width of 95% confidence interval for the point estimate, which means that the lower and upper bounds of the 95% confidence interval for the patient proportion of interest will be within 2.2% of the point estimate (point estimate +/- 2.2%). In addition, there will be approximately a 73% probability of identifying a least one AE with a true AE rate of 0.1%.

For an exploratory purpose, more calculations about the precisions of evaluating the CVR achievement percentage are also provided for difference sub-populations, such as HBeAg positive or Cirrhosis. Assuming HBeAg positive (Cirrhosis) is made of 54.5% (20%) of HBV patients, the percentage of patients achieving CVR is 80% and 3 -year drop-out rate is 35%, a sample size of N=2000 will have 1090 (400) patients in the interested group and about 708 (260) completers and a precision of no more than 0.029 (0.049) [You, 2016].

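### The adverse-event proportion takes no account of observation time although 35% are expected to leave by week 144, so read as a 3-year risk it is too low; the liver-event incidence has no stated estimator

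*Protocol*

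**What the plan says.** Protocol 9.3.4.4 states how AEs are to be summarised: by "dividing the number of subjects who experienced the AE during the treatment period by the number of subjects evaluable for safety analysis". No person-time or time-to-event summary of AEs is named.

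For liver outcomes the same section says: "The incidence of decompensated cirrhosis/liver disease and related complications, such as HCC, will be calculated for weeks of 48, 98 and 144", overall and "for certain sub-populations of interests, such as elderly and baseline Cirrhosis patients". It gives a population and time points, but no denominator, estimator or rule for patients who have left. (Week 98 is as printed; the primary endpoints use week 96. That is a separate matter.)

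Three other places determine how long patients are observed:
- 9.1.2 assumes that "the rate of loss-to-follow-up and discontinuation is 35" per cent, in a calculation for week 144.
- 8.2 lists among the events that count as withdrawal "Discontinuation of TDF (Viread, Beixin or Naxinde) for at least 28 days".
- 7.3 says: "Study participants will be followed up for 3 years or until they withdraw from the study".

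For patients already on TDF, the Schedule of Activities marks AE reporting from study entry and not at TDF initiation, while its note 6 anchors their follow-up months to the TDF start date. Inclusion criterion 4 keeps this group below 10% of the total.

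**The concern.** A patient who leaves after a few months can contribute an event only during those months, yet counts in the denominator as much as one followed for 36 months. The resulting figure depends on attrition as well as on the risk of the event.

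This matters for two reasons. The rationale (3.2) gives long-term effectiveness as the main aim and safety, in answer to physicians' concerns, as the second, so readers will be inclined to take the AE percentages as three-year risks. And section 12 proposes historical comparison with earlier trial data to offset the absence of a control group. A proportion that moves with drop-out cannot be set fairly against cohorts with different follow-up.

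The protocol also treats leavers unevenly. Its AE detection probability in 9.1.2 gives them no weight (shown below), whereas 9.3.4.4 gives them full weight. For benefit, 9.3.4.2 names Kaplan-Meier and Cox methods for time to CVR; for harm, no method that handles censoring is named.

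**Working it through.** **Inputs from the protocol.** N = 2000; 35% loss or discontinuation; CVR 80%; 95% confidence interval; true AE rate 0.1% with 73% detection (all 9.1.2).

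**The protocol's own figures.** Completers: 2000 × 0.65 = 1300. Precision: 1.96 × √(0.8 × 0.2 / 1300) = 0.0217, stated as 2.2%. AE detection: 1 − 0.999^1300 = 72.8%, stated as 73%. With all 2000 patients it would be 1 − 0.999^2000 = 86.5%, so the stated figure counts completers only.

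**Assumptions, not in the protocol.** Constant event rate λ over 3 years, drop-out unrelated to event risk, and four timings for the 35%. For a true 3-year risk R = 3.0%, λ = −ln(0.97)/3 = 0.01015 per year. For constant-hazard drop-out, μ = −ln(0.65)/3 = 0.1436 per year. Expected crude proportion:

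- Spread evenly: 0.65R + 0.35 × [1 − (1 − e^(−3λ))/(3λ)]
- Constant hazard: λ/(λ+μ) × (1 − e^(−3(λ+μ)))
- All at month 6: 0.65R + 0.35 × (1 − e^(−0.5λ))
- All at month 30: 0.65R + 0.35 × (1 − e^(−2.5λ))

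| Timing of drop-out | Share of 3 years observed | True 3.0% appears as | Shortfall |
|---|---|---|---|
| Spread evenly | 1 − 0.35/2 = 0.825 | 2.48% | 17.4% |
| Constant hazard | 0.35/0.4308 = 0.812 | 2.44% | 18.7% |
| All at month 6 | 0.65 + 0.35 × 0.5/3 = 0.708 | 2.13% | 29.1% |
| All at month 30 | 0.65 + 0.35 × 2.5/3 = 0.942 | 2.83% | 5.8% |

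(Shortfalls use unrounded values.)

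**Timing of events.** If events fall only in year 1 at an even rate and drop-out is spread evenly, the shortfall is 0.35 × (1/3)/2 = 5.8%; with constant-hazard drop-out it is 6.9%. If events fall only in the first six months, it is about 3%. The 6% to 29% range therefore describes the main scenarios and is not a bound.

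**Worked example, and what a rate recovers.** Take λ = 0.02 per year (assumed) with constant-hazard drop-out. The true risk is 1 − e^(−0.06) = 5.82%. The crude proportion is 0.02/0.1636 × (1 − e^(−0.4908)) = 4.74%, which is 18.6% low. Mean time to first event or exit, capped at 3 years, is (1 − e^(−0.4908))/0.1636 = 2.37 years. The rate is 0.0474/2.37 = 2.0 per 100 patient-years, the value put in.

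**Sub-groups.** The protocol assumes 35% drop-out for both groups it sizes: 0.65 × 1090 = 708.5 HBeAg-positive completers (stated as about 708) and 0.65 × 400 = 260 with cirrhosis. With equal drop-out and equal timing, a true 5% appears as 4.13% in both (spread evenly), so the contrast is preserved. Only if drop-out differed would it move. With an assumed 20% versus 50%, the same true 5% appears as 4.50% versus 3.76% (spread evenly) or 4.49% versus 3.62% (constant hazard), a spurious ratio of about 0.84 or 0.81.

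**The case against.** The strongest reply is that a crude on-treatment AE proportion is a standard descriptive summary. Section 9.1.1 calls the study descriptive, AEs are an exploratory objective, and the protocol nowhere calls the proportion a 3-year risk. For patients who stop TDF, later time lies largely outside the treatment period anyway. The safety-evaluable set is not defined; if it follows 9.2, patients with no post-baseline assessment drop out of the denominator, which shrinks the shortfall somewhat. Only spontaneous AEs related to the sponsor's products are collected, so under-reporting may matter more than the denominator. The renal question is answered mainly by the eGFR and phosphate analyses in 9.3.3. Time on TDF will be summarised (9.3.4.3), and further detail is left to the Reporting and Analysis Plan.

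All of this limits the point without removing it. The head-count rule is written in the protocol, so this is a stated choice and not an omission.

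Three stronger readings are tempting and not supported:
- A reader might infer that liver events are also divided by a head count, because their incidence "will be calculated for weeks of 48, 98 and 144, for the overall analysis population". That names a population, and Kaplan-Meier or cumulative incidence would be compatible with it.
- A reader might take 18% as the size of the error. It holds only under a constant event rate and drop-out spread over three years. The protocol's background places eGFR and BMD reductions mainly early in treatment, which would make the shortfall smaller for such events.
- A reader might infer that sub-groups are not comparable. The protocol states no unequal drop-out, and 9.3.4.4 names elderly and cirrhosis splits for liver events only, not for AEs.

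**Conclusion.** The point stands in limited form. Read as a 3-year risk, the AE proportion of 9.3.4.4 is too low given the protocol's own 35%. The central figure is about 18%, with about 6% to 29% under the other timings examined; all of these rest on assumed timing of events and drop-out and on non-informative drop-out. Read only as an on-treatment count, the proportion is not wrong, but it is poorly suited to the historical comparison in section 12.

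For decompensation and HCC the estimator is open. A head count would carry the same bias, and would distort the elderly and cirrhosis results only if drop-out there differs. The pre-entry time of patients already on TDF is a minor addition, given the cap below 10%.

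This is an inexpensive improvement to the reporting of harm. It does not affect the primary analyses.

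**What to change.** In 9.3.4.4, or in the Reporting and Analysis Plan with a matching sentence in the protocol:

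- Keep the crude AE and SAE proportions and add exposure-adjusted rates: first events per 100 patient-years, counted from study entry to first event, withdrawal or last contact.
- Report decompensation and HCC at each time point as Kaplan-Meier or competing-risk cumulative incidence, with censoring at last observation. For patients already on TDF, use time since TDF start with delayed entry at the study-entry date.

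TDF start, treatment duration and reasons for discontinuation are already collected, so the cost is wording and a few tables. The drawbacks are small: rates are less familiar than percentages, and a rate averages over time, so it should be read with care where events cluster early. The bias is removed only if drop-out is unrelated to event risk, and neither measure corrects under-reporting of spontaneous AEs.
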